#### **3.1** Primary Effectiveness Endpoints

Subject teeth in the Treatment Complete cohort that are healed or are healing at the twentyfour month Follow-up Visit.

Healed is defined by absence of a radiographic indication of apical periodontitis (PAI <3) and absence of clinical signs and symptoms.

Healing is defined by a reduction of radiolucency (if radiolucency is present at Baseline) and/or reduction of clinical signs and symptoms (if clinical signs and symptoms are present at Baseline)

Secondary analysis will be performed after all Treatment Complete subjects have completed the 12 month Follow-up Visit.

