Note: A Protocol Deviation CRF will not be completed if PAI score was not completed by an independent reviewer for a particular visit. In addition there is no defined study window for completion of PAI scoring by an independent reviewer.

- 7. Dental Cone Beam Computed Tomography (CBCT) X-rays, as applicable
- 8. Intra-Oral Examination including, but not limited to:
  - a. Tooth Number: Based on the Universal Tooth Numbering System (1-32)
  - b. Oral Hygiene: Oral hygiene should be graded on a score of Poor, Fair, or Good.
    - Poor:

There is evidence of: generalized inflammation and swelling of gingival tissue, generalized bleeding on probing and/or generalized plaque/ calculus accumulation

• Fair:

There is evidence of: localized mild to moderate inflammation of the gingival tissue, mild localized swelling of the gingival tissue, localized plaque/calculus accumulation and/or localized bleeding on probing

• Good:

There is evidence of: healthy gums and Minimal plaque. No evidence of gingival inflammation and no bleeding on probing.

c. Subject Tooth Assessments including:

- i. Probing Pocket Depth: The distance between the height of the free gingival margin and the height of attachment apparatuses below (bone, cementum, and periodontal ligament). Using a calibrated periodontal probe, the periodontal pocket depth should be recorded on the mesial, middle, and distal aspects of both the buccal and lingual sides of the tooth
- ii. Mobility
  - None: No distinguishable sign of movement.
  - Class I: The first distinguishable sign of movement greater than normal.
  - Class II: Horizontal tooth movement no greater than 1 mm.
  - Class III: Horizontal tooth movement greater than 1 mm, with or without the visualization of rotation or vertical depressability.
  - Any mobility other than none should be considered abnormal.
- iii. Swelling: This assessment includes the type and location of swelling.
- iv. Soft Tissue Lesions: This assessment includes the lesion presence, color and size where applicable. This assessment shall also include ulcerations and fistula/sinus tract.
- v. Cold Test
  - Normal: A sensation is felt, but disappears immediately upon removal of the stimulus
  - Negative: Lack of response to stimulus
  - Lingering: Lingering or intensification of a painful sensation after the stimulus is removed
  - Immediate: Excruciating, painful sensation as soon as the stimulus is placed on the tooth

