  - Delayed: A painful sensation is felt after an initial delay
- vi. Root Resorption
- vii. Furcation Involvement/Furcation Defect
  - Class I: The furcation can be probed, but not to a significant depth.
  - Class II: The furcation can be entered into but cannot be probed completely through to the opposite side.
  - Class III: The furcation can be probed completely through and through.
  - Class IV: The furcation can be probed through and through, and recession reveals a visible furcation.
- 9. Endodontic Assessments including:
- a. Pulp Diagnosis:
  - Normal Pulp: A clinical diagnostic category in which the pulp is symptomfree and normally responsible to pulp testing.
  - Reversible Pulpitis: A clinical diagnosis based on subjective and objective findings indicating that the inflammation should resolve and the pulp return to normal.
  - Symptomatic Irreversible Pulpitis: A clinical diagnosis based on subjective and objective findings indicating that the vital inflamed pulp is incapable of healing. Additional descriptors: lingering thermal pain, spontaneous pain, referred pain.
  - Asymptomatic Irreversible Pulpitis: A clinical diagnosis based on subjective and objective findings indicating that the vital inflamed pulp is incapable of healing. Additional descriptors: no clinical symptoms but inflammation produced by caries, caries excavation, trauma.
  - Pulp Necrosis: A clinical diagnostic category indicating death of the dental pulp. The pulp is usually nonresponsive to pulp testing.
  - b. Periradicular Tests (Percussion and Palpation):
    - None (-): No discomfort at all.
    - Mild (+): Little discomfort, but may be noticeable by the patient.
    - Moderate (++): Some noticeable discomfort.
    - Severe (+++): Definitive discomfort.
  - c. Periradicular Diagnosis:
    - Normal Apical Tissue: Teeth with normal periradicular tissues that are not sensitive to percussion or palpation testing. The lamina dura surrounding the root is intact, and the periodontal ligament space is uniform.
    - Symptomatic Apical Periodontitis: Inflammation, usually of the apical periodontium, producing clinical symptoms including a painful response to biting and/or percussion or palpation. It might or might not be associated with an apical radiolucent area.

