    - i. Probing Pocket Depth: The distance between the height of the free gingival margin and the height of attachment apparatuses below (bone, cementum, and periodontal ligament). Using a calibrated periodontal probe, the periodontal pocket depth should be recorded on the mesial, middle, and distal aspects of both the buccal and lingual sides of the tooth
    - ii. Mobility

- None: No distinguishable sign of movement.
- Class I: The first distinguishable sign of movement greater than normal.
- Class II: Horizontal tooth movement no greater than 1 mm.
- Class III: Horizontal tooth movement greater than 1 mm, with or without the visualization of rotation or vertical depressability.
- Any mobility other than none should be considered abnormal.
- iii. Swelling: This assessment includes the type and location of swelling.
- iv. Soft Tissue Lesions: This assessment includes the lesion presence, color and size where applicable. This assessment shall also include ulcerations and fistula/sinus tract.
- v. Root Resorption
- vi. Furcation Involvement/Furcation Defect
  - Class I: The furcation can be probed, but not to a significant depth.
  - Class II: The furcation can be entered into but cannot be probed completely through to the opposite side.
  - Class III: The furcation can be probed completely through and through.
  - Class IV: The furcation can be probed through and through, and recession reveals a visible furcation.
- 7. Endodontic Assessments including:
  - a. Periradicular Tests (Percussion and Palpation)
    - None (-): No discomfort at all.
    - Mild (+): Little discomfort, but may be noticeable by the patient.
    - Moderate (++): Some noticeable discomfort.
    - Severe (+++): Definitive discomfort.
  - b. Periradicular Diagnosis:
    - Normal Apical Tissue: Teeth with normal periradicular tissues that are not sensitive to percussion or palpation testing. The lamina dura surrounding the root is intact, and the periodontal ligament space is uniform.
    - Symptomatic Apical Periodontitis: Inflammation, usually of the apical periodontium, producing clinical symptoms including a painful response to biting and/or percussion or palpation. It might or might not be associated with an apical radiolucent area.
    - Asymptomatic Apical Periodontitis: Inflammation and destruction of apical periodontium that is of pulpal origin, appears as an apical radiolucent area, and does not produce clinical symptoms.

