## 13.4 Method for the Analysis of Primary Effectiveness Parameter

The primary effectiveness analysis will be based on Healing at twenty-four (24) months for Treatment Complete Cohort.

The proportion of subjects with healing, along with the exact 95% confidence interval, will be provided for healing at 24 months.

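### The healing definition lets the loss of baseline pulpal pain count as primary success, so a symptom-free tooth with an unchanged or new apical lesion can be scored as healing

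*Combined protocol and SAP*

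**What the plan says.** The primary endpoint in Section 3.1, repeated in the synopsis, is "Subject teeth in the Treatment Complete cohort that are healed or are healing" at month 24. Section 13.4 confirms the time point and cohort: "The primary effectiveness analysis will be based on Healing at twenty-four (24) months for Treatment Complete Cohort".

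- Healed is strict: "absence of a radiographic indication of apical periodontitis (PAI <3) and absence of clinical signs and symptoms".
- Healing is looser. It asks for less radiolucency, if there was any at Baseline, "and/or reduction of clinical signs and symptoms (if clinical signs and symptoms are present at Baseline"). Neither section says which signs and symptoms qualify, how large a reduction must be, or how a tooth that improves on one finding and not on another is scored.

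The Baseline exam in Section 7.4.4 records pulpal pain. The Cold Test has painful categories, among them "Lingering: Lingering or intensification of a painful sensation after the stimulus is removed". Symptomatic irreversible pulpitis is characterised by "Additional descriptors: lingering thermal pain, spontaneous pain, referred pain", while the asymptomatic form is the one without clinical symptoms. The protocol therefore treats pulpal pain as a clinical symptom.

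The itemised follow-up list in Section 7.17.2 repeats "Periradicular Tests (Percussion and Palpation"), swelling, soft tissue lesions including sinus tract, periradicular diagnosis and the McGill form. It does not list the Cold Test or Pulp Diagnosis.

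**The concern.** The endpoint is meant to show that apical disease has resolved or is resolving. Section 2.3 says that a healing endpoint should combine radiographic and clinical findings, with PAI 1 or 2 and no signs or symptoms. Pulpal pain is a different matter: once the pulp is out, its source is gone. The protocol does not say so in terms, but Section 2.2.2 treats removing the pulp as a purpose of root canal therapy, and Section 2.5 says that the treatment removes organic tissue from the canal system.

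For a tooth that was painful because its pulp was inflamed, the symptom limb of healing may then record only that the pulp was removed, which any root canal treatment aims to do. These teeth belong to the target population: Section 2.1 names the irreversibly inflamed pulp as an indication, and Section 5.1 admits any first or second molar indicated for treatment. In a single-arm study against a fixed 70%, successes gained in this way feed directly into the test.

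**Working it through.** **Step 1: the plan's own figure.** Inputs from Section 13.1: n = 86 evaluable, null rate 0.70, alternative 0.85, two-sided binomial test at 5%.

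- Smallest upper rejection limit with tail at most 2.5%: P(X ≥ 69 | 0.70) = 0.0223, whereas P(X ≥ 68 | 0.70) = 0.0396. The rule is to reject at 69 or more.
- Power: P(X ≥ 69 | 0.85) = 0.914, in line with the stated figure of about 90%.
- Enrolment: 86 / (1 − 0.20) = 107.5, rounded up to 108, as stated.
- The exact 95% interval in Section 13.4 agrees with the rule: 69/86 has lower limit 70.2%, 68/86 has 69.0%.

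The sample size calculation is not in dispute.

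**Step 2: scoring teeth against Section 3.1.** Two readings of the joining words are possible. On the inclusive reading either limb suffices. On the strict reading every limb whose baseline condition holds must be met.

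| Tooth | Baseline | Month 24 | Healed? | Healing, inclusive | Healing, strict |
|---|---|---|---|---|---|
| 1 | lingering cold pain, PAI 4 | no symptoms, PAI 4 unchanged | no | yes | no |
| 2 | lingering cold pain, no radiolucency | no symptoms, new lesion, PAI 4 | no | yes | yes |
| 3 | lingering cold pain, percussion ++, PAI 2 | percussion ++, PAI 2 | no | undetermined | undetermined |

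Tooth 2 passes on either reading. The radiolucency limb does not apply because there was no lesion at Baseline, the symptom limb is met, and no clause bars a new lesion. Tooth 3 cannot be scored because no rule combines a resolved finding with a persistent one.

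**Step 3: size.** Assume that true success under a combined radiographic and clinical definition equals the null, 70%, and that a share s of the failing teeth is reclassified as healing through baseline pulpal symptoms. The documents do not give s.

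Recorded rate = 0.70 + 0.30 × s. Expected true failures = 0.30 × 86 = 25.8, so reclassified teeth = 25.8 × s.

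| s | Teeth reclassified | Recorded rate | P(X ≥ 69) |
|---|---|---|---|
| 0 | 0 | 70% | 2.2% |
| 10% | 2.6 | 73% | 7.9% |
| 20% | 5.2 | 76% | 21.6% |
| 30% | 7.7 | 79% | 45.1% |

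The result depends on the assumed true rate. If that is 60%, s = 30% gives 0.60 + 0.40 × 0.30 = 72%, and the chance of rejection is 5.3%.

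**The case against.** **The strict reading is natural.** Each limb carries its own baseline condition, so one may say that every applicable limb must be met. Tooth 1 then fails. This is a fair reading, but the text does not fix it, and it leaves tooth 2 a success.

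**Follow-up testing.** A reader might infer that pulpal pain is never tested after Baseline. The documents do not support that. The synopsis lists Cold Test and Pulp Diagnosis among the endodontic assessments, Section 8.0 schedules general dental and endodontic assessments at 6, 12, 18 and 24 months, and the analgesic paragraph of Section 7.17.2 names a cold test. Only the itemised list omits it. The McGill form also re-measures pain at every follow-up visit. What stands is an inconsistency to reconcile. Retesting would not close the gap, since a negative cold test at month 24 would simply document the reduction.

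**Every tooth with symptomatic pulpitis.** A reader might also infer that every such tooth is scored healing whatever its periapical state, so that affected teeth respond at 100%. Tooth 3 shows why not: with persisting tenderness, pain, swelling or a sinus tract, the status is undetermined. The firm case is the symptom-free tooth with a lesion.

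**The share s may be small.** Section 2.3 says that success is lower when a periapical lesion is present, and Section 7.4.4 says that necrotic pulps usually do not respond to testing. Failures may therefore concentrate in teeth without cold pain. This stands, and it is why the figures are upper-end.

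**The null.** How far the rate is inflated relative to 70% depends on the definition of success behind that figure. Section 2.3 says that definitions in the literature differ, and the literature report was not available for this check.

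**Mobility.** One might argue the reverse error: a sound tooth with stable Class I mobility, which Section 5.2 admits, could be neither healed nor healing because "Any mobility other than none should be considered abnormal". That sentence belongs to an examination scale. Nothing makes stable mobility a clinical sign for this endpoint, so the inference is weak and forms no part of this point.

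**Conclusion.** The concern holds in a limited form. As written, healing can be met by a reduction of any baseline clinical sign or symptom, and pulpal symptoms are not excluded. A symptom-free tooth that had pulpal pain at Baseline counts as a primary success with an unchanged lesion on the inclusive reading and with a new lesion on either reading. The direction of bias is upward.

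The size cannot be known from the documents. At a true rate of 70%, reclassifying about 3 to 8 of some 26 failing teeth (s from 10% to 30%) would raise the chance of a false claim of superiority from 2.2% to between 7.9% and 45.1%. These figures assume that every tooth in the share s is scored healing. The point also rests on the clinical inference that pulpal pain resolves with pulp removal. It does not show that the study would reach a false conclusion, only that the rule permits wrong successes and should be tightened.

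**What to change.** In Section 3.1 and the synopsis:

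1. For healing, state that the qualifying signs and symptoms are periradicular ones recorded at both Baseline and month 24: percussion, palpation, swelling, and sinus tract or soft tissue lesion at the subject tooth. State that Cold Test, Pulp Diagnosis and thermal or pulpal pain do not count.
2. Replace the and/or with a rule that every limb applicable at Baseline must improve, and that month 24 shows no new or larger radiolucency and no new or worse periradicular finding. A tooth with no applicable limb can then succeed only as healed.
3. Leave healed as it is, requiring both PAI below 3 and freedom from clinical signs and symptoms, and make explicit that patient-reported pain or pain on biting at the subject tooth counts there. The shorter list in item 1 must not be carried into healed, or a tooth with persisting pain could qualify.
4. Reconcile the synopsis assessment list, Section 7.17.2 and Section 8.0 on whether the Cold Test is a follow-up assessment.

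The cost is wording only: the listed findings and the PAI are already scheduled at Baseline and at every follow-up visit. The downside is that some teeth now scored as healing become failures.

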#### **3.2** Primary Safety Endpoints

Incidence of device related adverse events as defined by perforation, instrument separation, root fracture, sodium hypochlorite accident, or Gutta Percha extrusion, as related to the device for the Treatment Complete cohort.

#### **3.3 Secondary Endpoints**

The following outcomes will be assessed:

- 1. McGill Short Form Pain Questionnaire
- 2. Gracely Descriptor Differential Scale (DDS) 59
- 3. Patient Satisfaction Survey
- 4. AAE Case Difficulty Assessment
- 5. Soft Tissue Lesions
- 6. Swelling
- 7. Root Canal Therapy Retreatment
- 8. Treatment Time
- 9. Procedure Time
- 10. Periapical Index (PAI) analyzed utilizing radiographic analysis by independent reviewer
- 11. Cone Beam Computed Tomography (CBCT) Sub-Set Evaluation
- 12. Additional Radiographic Analysis may be completed

## 4.0 STUDY DESIGN

A prospective, non-significant risk device, literature controlled, study evaluating healing rates for the Sonendo GentleWave System in the treatment of 1st and 2nd molars indicated for root canal therapy.

All patients will receive root canal therapy with the Sonendo GentleWave System. All patients will be followed for 24 months post procedure.

#### 5.0 STUDY POPULATION

Up to 120 subjects, aged 18 to 75 years, who have a 1st or 2nd molar tooth indicated for root canal therapy, will be enrolled in the study.

#### 5.1 Pre-Procedure Inclusion Criteria

- 1. The patient is 18 to 75 years of age
- 2. The subject tooth is indicated for root canal therapy
- 3. The subject tooth is a 1st or 2nd molar
- 4. The patient is mentally and physically able and willing to fully comply with this protocol, including adhering to the follow-up schedule and completing forms and questionnaires
- 5. Signed Informed Consent Form

#### 5.2 Pre-Procedure Exclusion Criteria

- 1. Poor oral hygiene according to a Poor, Fair, Good Scale
- 2. Subject tooth with  $\geq$  Class II Mobility
- 3. Subject tooth with Periodontal Pocket Depth  $\geq 6$
- 4. Periodontal probe reaches the apex of the subject tooth
- 5. Furcation involvement originating from periodontal disease, on the subject tooth, one and/or two adjacent teeth in direct contact with the subject tooth
- 6. Subject tooth with  $\geq$  Class III endodontic furcation involvement
- 7. Subject tooth with open or incompletely formed root apices
- 8. Vertical fracture, horizontal fracture, or perforation extending below the Cemento-Enamel Junction (CEJ) of the subject tooth
- 9. Caries or another condition of the subject tooth that
  - a. prevents adequate seal of the device
  - b. requires a separate procedure for crown lengthening
  - c. requires a post

- d. provides inadequate biological width for crown retention
- 10. Any dental treatment on the subject tooth completed with the known use of devitalizers or formocresol
- 11. Subject tooth having previous or attempted pulpectomy or root canal therapy
- 12. One or two adjacent teeth in direct contact with the subject tooth requiring root canal therapy, pulpectomy or pulpotomy
- 13. Any tooth on the same side of the oral cavity as the subject tooth with a source of pain
- 14. Extraoral swelling on or around the subject tooth that has not undergone antibiotic treatment or a procedure to treat the swelling prior to RCT
- 15. Any condition that would preclude tolerance of a root canal therapy including but not limited to being in a reclined and prolonged position in a dental chair, use of a dental dam, or ability to have an open mouth for extended periods of time (>15 minutes) (e.g. history of seizure within the last 5 years, severe asthma, or extreme gag reflex)
- 16. Any other condition that the Investigator determines is unacceptable for enrollment into the study
- 17. Nonodontogenic facial pain
- 18. History of cancer within the oro-maxillofacial region
- 19. History of any cancer within the last two years, including skin cancer
- 20. History of head and/or neck radiation therapy
- 21. Immunocompromised patients (i.e. corticosteroid usage)
- 22. Any medical history that affects blood coagulation (e.g. bleeding disorders)
- 23. Long-term or current usage of medication that affects blood coagulation. This includes herbal or other over the counter medications. Exception: Patients taking daily low dose Aspirin (81mg) or patients that can stop Aspirin or Ibuprofen products three (3) days prior to procedure, should not be excluded from the study.
- 24. Patients with any medical condition causing chronic pain (e.g. spinal injury)
- 25. Patients on long-term (i.e. more than three months) narcotic, opioid, or other similar analgesic (e.g. daily narcotic pain medication for spinal disease)
- 26. Any infectious diseases (e.g. HIV, Hepatitis B, Hepatitis C, Tuberculosis, BCE, or Prion diseases)
- 27. Uncontrolled diabetes or diabetics with unknown hemoglobin A1c levels
- 28. A known allergy to local anesthetics, titanium carbon-nitride or stainless steel

- 29. A pacemaker, implantable cardiac defibrillator (ICD), or other implanted electronic medical device
- 30. Patient is institutionalized, a prisoner, homeless, or on active military duty
- 31. Patients with documented current alcohol and/or drug abuse
- 32. Patient is pregnant or planning to become pregnant within the duration of the study
- 33. Participated in any clinical study in the past 30 days

## 5.3 Intra-Procedure Inclusion Criteria

- 1. Successful removal of caries on the subject tooth
- Successful completion of build-up to restore the subject tooth crown when used in combination with the Occlusal Plate.
   *Exception*: This does not apply when the Tooth Cap is utilized.

#### 5.4 Intra-Procedure Exclusion Criteria

- 1. Use of laser devices
- 2. Subject tooth that requires crown lengthening
- 3. Subject tooth that requires a post
- 4. Subject tooth that provides inadequate biological width for crown retention
- 5. Perforation of the subject tooth
- 6. Vertical fracture or horizontal fracture below the Cemento-Enamel Junction (CEJ) of the subject tooth
- 7. Internal or external root resorption that affects the use of Sonendo GentleWave System

#### 6.0 DENTAL CONE BEAM CT SUB-SET

Dental cone beam computed tomography (CBCT) systems are a variation of traditional cone beam systems. The CBCT systems used by dental professionals rotate around the patient, capturing data using a cone-shaped X-ray beam. These data are used to reconstruct three-dimensional (3D) images of the patient's dental anatomy (teeth).

Subjects enrolled in the study may be included in a CBCT subset. All subjects that have access to the clinical sites with CBCT scanners may be included in the subset.

